6.11. Subgroup Analyses

The following subgroups will be analyzed using data collected prior to permanent discontinuation of IP to evaluate consistency of results on the primary efficacy measure if there are sufficient numbers of participants by subgroup (for example, 10%):

- age (<65 years, ≥ 65 years)

- baseline HbA1c ($\leq 8\%$, $> 8\%$)
- participant's prior personal CGM use (yes/no)
- participant's SGLT2 use (yes/no)
- participant's injectable GLP-1 use (yes/no)
- prandial dosing plan (carbohydrate counting, fixed dose)
- sex (male or female)
- BMI ($< 30, \geq 30$; $< 35, \geq 35 \text{ kg/m}^2$)
- duration of diabetes (using the median as the cutoff)
- race
- ethnicity

Analyses for primary efficacy measure will be performed using an MMRM model that includes the same fixed effect and covariate given for the primary analysis model plus factors of subgroup and 2-way interaction of subgroup and visit. The effect of subgroup at the primary endpoint (Week 12) will be evaluated to assess subgroup effect.

Additional subgroup analyses may also be performed.

6.12. Interim Analyses

No interim analyses are planned for this study. If an unplanned interim analysis is deemed necessary for reasons other than a safety concern, the protocol must be amended.

Appendix 1. Derivation of CGM Variables

General Derivation Specifications

All CGM variables will be derived for each patient, for each valid CGM day and also overall for baseline (Week -2-0), Visit 7 (Week 2-4), Visit 9 (Week 6-8), and Visit 12 (Week 10-12).

No missing CGM values will be imputed.

Since the CGM values may not be measured at the exact same time for each day for a specific individual patient, due to device changes or gaps in usage, non-overlapping intervals ('buckets') of 15 minutes over 00:00:00 to 23:59:59 (00:00:00 to 00:14:59, 00:15:00 to 00:29:59, etc.) will be used for any derivations requiring time-matched measurements across days within a visit.

All CGM glucose derivations will be conducted in units of mg/dL and will be converted to mmol/L by multiplying by 0.0555.

Only readings from valid CGM days (defined in Section 6.10.1) collected during the entire baseline period and treatment period will be included in derivations, excluding data (if any) that are collected while patients temporarily are off study treatment.

Glucose in Target Ranges, Hypoglycemia- or Hyperglycemia

The percentage of time within a glucose range (target, hypo- or hyperglycemia ranges) will be calculated as the number of observations within the specified range divided by the number of observations in the time interval (e.g., 24-hour period). The duration (in minutes) within the glucose range will then be calculated as the percentage of time within the glucose range times the length of the period (24 hours, 18 hours, for the periods of 24-hour or daytime respectively).

For example, if a patient had a total of 5 observations with glucose values <70 mg/dL (3.9 mmol/L) out of a total of 90 observations recorded in a 24-hour period, the percentage of time spent in hypoglycemia during the 24-hour period for this patient will be calculated as 5/90 = 5.6%. The duration (in minutes) with hypoglycemia (glucose value <70 mg/dL [3.9 mmol/L]) during this 24-hour period for this patient will be calculated as the percentage of time within the glucose range times the length of the period 1440 minutes (24 hours), (i.e., 5/90*1440 = 80 minutes).

Incremental Area under the Glucose Curve (iAUC)

iAUC_{0-T} will be calculated as the average value of iAUC on all valid CGM days during that visit with sufficient data to calculate the iAUC_{0-T} (Section 6.10.1). For each day, iAUC_{0-T} will be calculated as the sum of areas of all individual trapezoids within the time frame according to the formula:

$$iAUC_{0-T} = \sum_{i=1}^k A_i = \sum_{i=1}^k \frac{(G_i - G_0) + (G_{i-1} - G_0)}{2} \Delta t_i$$

where A_i is area of the respective trapezoid, G_i is glucose concentration at a particular time, G_0 is the starting glucose concentration before the start of the meal, Δt is the time interval between consecutive CGM values, which should be always 15 minutes unless missing data occur, and k is the total number of intervals within the time frame 0-T, and T could be 1 hr, 2 hr, 3 hr or 4 hr. If the intermediate time points are missing, the next available time point will be used in calculating the trapezoid area. Also since it is possible that $G_i < G_0$ or $G_{i-1} < G_0$, A_i could also be negative.

G_0 , the starting glucose concentration, will be calculated as the average of the CGM values in the time window [-29, 0] mins relative to the start of the meal (at most 2 CGM values); G_k , the last glucose concentration, is defined as the CGM values in the window [0, +14] minutes relative to the last time point of the time frame. For example, to calculate iAUC_{0-2hr} after the start of breakfast, G_k will be the CGM values in the window [0, +14] minutes relative to the 2 hours after the start of breakfast. The derivation of each iAUC_{0-T} will require that G_0 and G_k values are both available and will exclude data collected after the next meal event.

Mean Sensor Glucose Excursions

Mean sensor glucose excursions 0 to T hour(s) in a valid postmeal time interval will be calculated by averaging all excursion values within the time interval 0-T, excluding data collected after the next meal event, where excursions are defined as $G_i - G_0$ as defined in iAUC.

Glucose Variability

Glycemic variability will be evaluated using the notation below:

- i represents a time point within a time period (a 24-hour period, daytime or nighttime)
- n represents the number of time points within the time period
- k represents a day within a visit
- m represents number of days CGM is performed at a visit
- $BG_{k,i}$ represents the glucose value at time point i on day k

Within-Day Variability

For variables assessing within-day variability, first determine the variability within each day, then average across days within a visit.

Within-day glucose standard deviation (SD) (Hirsch 2005; Rodbard 2009):

$$SD = \frac{1}{m} \sum_{k=1}^m SD_k = \frac{1}{m} \sum_{k=1}^m \sqrt{\frac{\sum_{i=1}^n (BG_{k,i} - \left\{ \frac{\sum_{i=1}^n BG_{k,i}}{n} \right\})^2}{n-1}}$$

Within-day glucose coefficient of variation (CV) (Clarke 2009):

$$CV = \frac{1}{m} \sum_{k=1}^m CV_k = \frac{1}{m} \sum_{k=1}^m \frac{SD_k}{\left(\frac{\sum_{i=1}^n BG_{k,i}}{n} \right)} \times 100$$

Between-Day Variability

For variables assessing between-day variability, first determine the variability for each time points across days within a visit then average across all time points.

Between-day glucose standard deviation (SD) (Rodbard 2009):

$$SD = \frac{1}{m} \sum_{k=1}^m SD_k = \frac{1}{m} \sum_{k=1}^m \sqrt{\frac{\sum_{i=1}^n (BG_{k,i} - \left\{ \frac{\sum_{i=1}^n BG_{k,i}}{n} \right\})^2}{n-1}}$$

Between-day glucose coefficient of variation (CV):

$$CV = \frac{1}{n} \sum_{i=1}^n CV_i = \frac{1}{n} \sum_{i=1}^n \frac{SD_i}{\left(\frac{\sum_{k=1}^m BG_{k,i}}{m} \right)} \times 100$$

In addition to the CGM outcomes above, SD and CV in the daily mean values will also be derived.

Overall Variability

The CV, SD will be calculated using the standard formulas across collected across all valid days for time interval in treatment period (Week 0-12).

Highest Postprandial Glucose

Highest postprandial glucose level excursions within 4 hours after meals, will be calculated as the maximum glucose value during 0 to 4 hours after start of meal, truncating the data at the next meal event.

Leo Document ID = 6d036fcc-92be-485e-97ac-2686aa6c5908

Approver: PPD

Approval Date & Time: 27-Oct-2020 15:59:47 GMT

Signature meaning: Approved

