8.1.1. Continuous Glucose Monitoring

The unblinded FreeStyle Libre 14-day CGM system will be used by all study participants from Visit 2 to Visit 12. This is an FDA-approved CGM system indicated for replacing blood glucose testing and detecting trends and tracking patterns aiding in the detection of episodes of hyperglycemia and hypoglycemia, facilitating both acute and long-term therapy adjustments in persons (age 18 and older) with diabetes.

Participants will use the:

- FreeStyle Libre sensor
 - The sensor can be worn for up to 14 days. Participants will be instructed to change the sensor according to the product information.
- FreeStyle Libre reader:
 - for participants to scan the sensor and for sites to upload CGM data to the CGM vendor
 - The reader also has a built-in blood glucose meter.
- LibreLink application (app) on a study-provided mobile device
 - for participants to scan the sensor and for sites to have remote access to CGM data for telephone visits and as clinically indicated
- Participants will be able to review CGM data for daily diabetes management with the reader and/or app.

Participants will receive training on the use of the system according to product information, and will be expected to complete the following study requirements:

- **Start each new sensor session with the reader first and then with the LibreLink app.**
- Change the sensor every 14 days or earlier if needed.
- Scan with the reader and app at least 4 times throughout the day (morning upon waking, prior to meals, bedtime) and as needed. After the start of a new sensor session, the sensor can be scanned with the reader and app in any order.
 - Make every effort to scan with the **reader and app** at least every 8 hours to avoid gaps in glucose data.
 - More frequent scanning is encouraged.
 - Participants should not ignore symptoms that may be due to hypoglycemia or hyperglycemia. Note that the FreeStyle Libre does not have alarms unless if the sensor is scanned.
- Participants should check sensor glucose readings with a blood glucose meter as instructed according to product information when the “Check Blood Glucose” symbol appears, when symptoms do not match sensor readings, or when readings are suspected to be inaccurate.

- The sensor must be removed before magnetic resonance imaging (MRI), computed tomography (CT) scan, X-ray, or diathermy treatment.
- Note and avoid substances that may interfere with sensor glucose readings including:

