6.10. Continuous Glucose Monitoring Analysis

6.10.1. General Considerations

The analyses described in this section will include data collected during the entire baseline period and treatment period. Percentage and duration in target range, hypoglycemia, hyperglycemia will be analyzed for baseline (Week -2-0), Visit 7 (Week 2-4), Visit 9 (Week 6-8), and Visit 12 (Week 10-12). Other CGM variables will be analyzed for baseline (Week -2-0) and Visit 12 (Week 10-12).

To ensure that the CGM outcome variables are only calculated from CGM session days with sufficient data within the 24-hour, daytime (0600 hours to midnight), or nighttime (midnight to 0600 hours) periods, the following criterion will be used to determine a valid CGM session day to be counted into the calculation for a visit: minimum number of measures per day – at least 70% of the total measures that are supposed to be obtained (i.e., 70% of the 96 measures) for the 24-hour period.

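### The SAP lets a meal window count for iAUC on its two end readings alone and bridges a gap of any length between them; the 24-hour 70% rule does not protect the window.

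*SAP*

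**What the plan says.** iAUC over 0-1 h and 0-2 h is listed among the other secondary endpoints (Protocol Section 3; SAP Table ITSW.4.1), outside the gated sequence. Protocol 9.4.3 leaves the analysis details to the SAP. SAP Appendix 1 sets these rules:

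- The starting value G_0 is the "average of the CGM values in the time window [-29, 0] mins relative to the start of the meal", at most two readings.
- The closing value G_k is the reading "in the window [0, +14] minutes relative to the last time point of the time frame".
- The spacing of readings is one "which should be always 15 minutes unless missing data occur".
- For gaps: "If the intermediate time points are missing, the next available time point will be used in calculating the trapezoid area".
- The derivation "will require that G_0 and G_k values are both available", and data after the next meal are excluded.
- The visit value is the average over valid CGM days with enough data for the iAUC. For what is enough, Appendix 1 points to Section 6.10.1.

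Section 6.10.1 contains a whole-day rule only: "the following criterion will be used to determine a valid CGM session day to be counted into the calculation for a visit", namely at least 70% of 96 readings over 24 hours. Two related measures in Appendix 1 are no tighter. Mean excursion refers to a valid interval after the meal without defining one, and highest postprandial glucose has no coverage requirement.

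**The concern.** A postprandial excursion rises and falls. If the readings around its top are missing and the remaining points are joined by a straight line, much of the area disappears, yet the window still counts as evaluable and enters the participant's mean with the same weight as a complete one. The reference to Section 6.10.1 looks like a safeguard, but a day can pass the 24-hour rule with a whole meal window empty.

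The study has one arm and compares Week 12 with baseline. No control group would absorb a difference in data completeness between the two periods, so any difference in how often windows are bridged goes into the reported change. The documents expect gaps: Protocol 8.1.1 asks participants to scan "at least every 8 hours to avoid gaps in glucose data", and SAP Appendix 1 mentions gaps in usage.

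**Working it through.** The plan states no iAUC value, curve, peak time or gap rate, so there is no figure of its own to reproduce here.

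**Step 1: can an empty window pass the day rule?** 70% of 96 = 67.2, so at least 68 readings are needed and 96 - 68 = 28 may be missing; 28 x 15 min = 420 min = 7 h. With 15-minute readings, a 0-1 h window has 3 interior readings and a 0-2 h window has 7. All of them can be lost on a valid day.

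**Step 2: size of the error in one window.** The SAP formula sums [(G_i - G_0) + (G_(i-1) - G_0)]/2 x dt. I applied it to assumed excursion curves with peak time p = 60, 75 and 90 min, 15-minute readings, and G_k taken at T. Percentage errors do not depend on peak height. The shapes are:

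- A: f(t) = (t/p)exp(1 - t/p)
- B and C: the square and cube of A (slower early rise)
- D: half-sine returning to zero at 2p
- E: triangle falling over 120 min
- F: triangle falling over p (symmetric)

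Worked example, shape A, p = 75, peak 60 mg/dL. Excursions at 0, 15, ..., 120 min are 0, 26.71, 43.73, 53.71, 58.63, 60.00, 58.95, 56.31, 52.69.

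- All readings: 15 x (358.04 + 52.69/2) = 5,766 mg/dL x min.
- End readings only: 120 x 52.69/2 = 3,161, which is -45%.
- 30-90 min lost: 15 x 26.71/2 + 90 x (26.71 + 56.31)/2 + 15 x (56.31 + 52.69)/2 = 4,753, which is -18%.

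Percentage error at p = 60 / 75 / 90:

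| Shape | 0-1 h, ends only | 0-2 h, ends only | 0-2 h, 30-90 min lost | 0-2 h, 15-45 min lost |
|---|---|---|---|---|
| A | -29 / -24 / -20 | -54 / -45 / -39 | -20 / -18 / -15 | -13 / -9 / -7 |
| B | -16 / -5 / +3 | -61 / -46 / -34 | -35 / -27 / -21 | -7 / -2 / +1 |
| C | -5 / +13 / +25 | -68 / -48 / -31 | -47 / -32 / -21 | -2 / +4 / +6 |
| D | -20 / -13 / -9 | -100 / -59 / -39 | -47 / -26 / -17 | -10 / -5 / -3 |
| E | 0 / 0 / 0 | -60 / -49 / -37 | -34 / -26 / -15 | 0 / 0 / 0 |
| F | 0 / 0 / 0 | -100 / -65 / -43 | -56 / -35 / -18 | 0 / 0 / 0 |

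The -56% comes from shape F at p = 60. With peak 60, the full area is 60 x 120/2 = 3,600. With 30-90 min lost it is 112.5 + 15 x 90 + 112.5 = 1,575, and 1,575/3,600 = 0.44. Without shape F the lower end of that column is -47%.

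The last column keeps the 60-minute reading. Losing only the single highest interior reading costs little at 0-2 h: the largest loss here is again shape F at p = 60, 15 x (60 - 45) = 225 of 3,600, about 6%.

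**Step 3: effect on a visit mean.** Assume 10% of windows in one period have end readings only and the others are complete, with equal true iAUC. The mean for 0-2 h then falls by 0.10 x 31% to 0.10 x 100%, that is 3% to 10%. For the worked example it is 0.10 x (5,766 - 3,161) = 260, or 4.5%. The 10% is illustrative. With the same pattern in both periods, the two shifts largely cancel in the change.

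**Step 4: the sibling measures.** Losing readings can only lower the highest value or leave it unchanged. Mean excursion can move either way: on shape A, losing the 15-45 min readings raises the 0-2 h mean excursion (time 0 excluded) by 5%, 12% and 16% for p = 60, 75 and 90.

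**The case against.** The requirement for both end values already screens out many long gaps. A gap that removes the premeal readings, or runs past the closing window, makes that iAUC non-evaluable. To leave only the two ends at 0-2 h, a gap must start just after the meal and finish at about two hours. Protocol 8.1.1 asks for at least four scans a day and for every effort to scan every 8 hours. Values are averaged over valid days, and the same rule applies at baseline and Week 12. All this stands. It limits how often the problem can occur and how far it reaches the change from baseline, but it does not supply a gap limit.

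Three stronger readings are tempting, and the documents do not support them.

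- A reader might infer that bridging always biases iAUC downward by a fixed percentage, for example 20-29% at 0-1 h. That figure belongs to one assumed curve (shape A) with every interior reading missing. With a peak at 60-90 min, no peak lies inside the 0-1 h window; the error there reflects the curvature of the early rise and can be zero or positive. The SAP also allows negative areas, so bridging over a dip below G_0 raises the result.
- A reader might infer from the 8-hour scanning instruction that a late scan typically erases the peak. The documents do not say that readings older than 8 hours are dropped. Even if they are, a lapse that removes only the first hour has the small effect shown in the last column.
- A reader might infer that gaps are common around meals. No gap rate is given.

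**Conclusion.** The point holds in a limited form. Appendix 1 is explicit that two readings suffice and that any gap between them is bridged; the day rule it cites does not protect the meal window. For every shape and peak time tried, iAUC 0-2 h is too low when all interior readings are lost (31-100%) or when the 30-90 minute readings are lost (about 15-56%). With only the first hour lost the error is about -13% to +6%. For iAUC 0-1 h, it runs from -29% to +25% with end readings only, so no direction can be claimed.

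These sizes rest on assumed curves peaking at 60-90 minutes and apply to a single affected window. The effect on the reported change depends on how often such windows occur and whether that differs between baseline and Week 12, which the documents do not tell us. The primary endpoint and the gated secondaries do not use this derivation. It is worth correcting because the remedy is cheap and, in a before-after design, a difference in completeness would otherwise be indistinguishable from a treatment effect on this endpoint.

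**What to change.** In SAP Appendix 1, define a valid postmeal window once:

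- a maximum gap between consecutive readings, for example 30 minutes (one missed reading);
- a minimum coverage, for example 70% of the 15-minute readings expected up to T or up to the next meal, whichever is earlier.

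The truncation matters for mean excursion and highest glucose, which the SAP cuts at the next meal. A next meal at 2.5 h leaves 10 of 16 readings (62.5%) of a 0-4 h window, so 70% of the full window would discard data the SAP means to keep.

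Apply the definition to iAUC, mean excursion (replacing its undefined valid interval) and highest postprandial glucose. Treat windows that fail as missing, and keep the next-available-reading bridge only for gaps within the limit. Report the number of windows bridged and excluded at baseline and at Week 12, so that a difference in completeness is visible. The 30 minutes and 70% are suggestions; what matters is that limits are fixed before the data are analysed.

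The cost is SAP wording and one programming check. The downside is that some meal windows are dropped; with up to 14 days per session most participants should keep enough, but the documents give no gap rate to confirm this.

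### As extracted, SAP Appendix 1 shows the within-day formula under between-day glucose SD, contrary to its own worded rule; check the source page and correct if confirmed (low severity, exploratory output only)

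*SAP*

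**What the plan says.** The Glucose Variability part of SAP Appendix 1 sets its notation first: "i represents a time point within a time period" and "k represents a day within a visit". The number of time points is n, and "m represents number of days CGM is performed at a visit".

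It then gives two worded rules. Within-day variability is found inside each day and averaged over days. For the other kind: "For variables assessing between-day variability, first determine the variability for each time points across days within a visit then average across all time points".

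Four formulas follow. As extracted:

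- **Within-day SD:** average over k = 1..m of SD_k; inner sum over i, centred on the daily mean, divisor n-1.
- **Within-day CV:** average over k of SD_k divided by the daily mean.
- **Between-day SD:** the same expression as within-day SD.
- **Between-day CV:** average over i = 1..n of SD_i divided by the mean over days at time point i.

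The general rules of the same appendix define 15-minute buckets that "will be used for any derivations requiring time-matched measurements across days within a visit", and state: "No missing CGM values will be imputed". SAP 6.8.3 sends both the within-day and the between-day SD and CV to ANCOVA as exploratory measures.

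**The concern.** One quantity has two incompatible definitions a few lines apart. A programmer who follows the sentence and one who follows the formula would report different variables under the same label.

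The formula version would duplicate the within-day SD. It could not register a change in how much a participant's glucose differs from one day to the next at the same clock time. It would instead report a change in the daily swing under a between-day name. A reader of the ANCOVA table would have no means of telling.

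**Working it through.** **1. Set the definitions side by side.**

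| | Inner spread taken over | Inner divisor | Outer average over |
|---|---|---|---|
| Worded between-day rule | days k | m-1 (by implication) | time points i |
| Between-day CV formula | uses SD_i and the mean over days k | not shown | time points i |
| Between-day SD formula, as extracted | time points i | n-1 | days k |
| Within-day SD formula | time points i | n-1 | days k |

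The last two rows are identical. The heading, the worded rule, the CV indexing and the provision of buckets for time-matching across days all point to the first row. Only the SD expression disagrees, and the SD_i needed by the CV is left without a definition.

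**2. Does the difference matter numerically?** The documents give no between-day SD to reproduce and no glucose profiles, so every profile here is assumed: m = 14 days, n = 96 readings per day, mg/dL. Each reading is a day level plus a sine wave of amplitude A with three full cycles per day. The day levels are 14 equally spaced values over 160 ± H.

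Formula as extracted: day levels cancel within a day, so the result is A × sqrt(n / (2(n-1))) = A × sqrt(96/190) = 0.7108 A.
- A = 40: 28.43
- A = 20: 14.22

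Worded rule: the daily wave cancels at a fixed time point, so the result is the SD of 14 equally spaced levels, (2H/13) × sqrt(14 × 15/12) = 0.6436 H.
- H = 40: (80/13) × 4.183 = 25.74
- H = 20: 12.87

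| Assumed case | Formula as extracted | Worded rule |
|---|---|---|
| Identical days (A = 40, H = 0) | 28.4 | 0 |
| Flat days, levels 120 to 200 (A = 0, H = 40) | 0 | 25.7 |
| Both (A = 40, H = 40) | 28.4 | 25.7 |
| Change when H goes from 40 to 20, A fixed | 0.0 | -12.9 |
| Change when A goes from 40 to 20, H fixed | -14.2 | 0.0 |

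**3. Is there a predictable direction?** The ratio of formula to rule is (0.7108/0.6436) × A/H = 1.104 × A/H. For A and H each in {10, 20, 40, 60} it runs from 0.18 (A = 10, H = 60) to 6.63 (A = 60, H = 10), and exceeds 1 in 10 of 16 cells. Four simulated settings with random noise (assumed within-day SD 20-40, day-level SD 10-30, residual SD 10-20) gave ratios from 0.80 to 3.00. No general direction follows, and the ranges depend on the values assumed.

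**4. Readings per bucket.** SAP 6.10.1 accepts a day with 70% of 96 measures: 0.70 × 96 = 67.2, so at least 68 readings and up to 28 empty buckets. With nothing imputed, the number of days contributing to SD_i can differ between buckets.

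**The case against.** **It may be an extraction fault.** The repeated expression sits in machine-read formulas. An author who wrote SD_i in the CV line would normally have defined it in the line above, and that is the line that appears duplicated. A lost original line would explain this as well as an author's copying slip would. This stands: the text cannot decide between the two, so the point has to begin with a check of the page. A reader might infer that an error in the SAP is established; the documents available do not show that.

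**The intent is already plain.** This is true, and it shows which side to correct. It does not remove the conflict if the page carries it. Two identical SD columns would be easy to notice, which lowers the risk.

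**Little depends on it.** This also stands. A reader might infer that the variability endpoint is compromised. Table ITSW.4.1 lists a CV, the between-day CV is correctly indexed, and Appendix 1 separately derives the SD and CV of daily means.

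**Missing readings are not a separate defect.** Computing an SD over the values present is the ordinary reading when nothing is imputed. Naming the count is a clarification.

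**Overall Variability.** That sentence names Week 0-12, whereas SAP 6.10.1 uses baseline and Visit 12 for other CGM variables. A reader might infer a lost baseline comparison. The documents do not support this: Week 0-12 may be a deliberate extra summary, the general rules can supply the other windows, and SAP 6.8.3 names only within-day and between-day measures for ANCOVA.

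**Conclusion.** The point holds conditionally and at low severity. In the text available, the between-day SD formula is the within-day formula and contradicts the worded rule above it. If the original page shows the same, programming it literally would make the two SDs equal for every participant, which follows from the algebra alone.

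The sizes above (0 against -12.9 mg/dL, and -14.2 against 0) rest on assumed profiles. They show that the two expressions measure different things; they do not estimate the impact in this trial. The consequence is limited to one exploratory ANCOVA output. The primary endpoint, the gated endpoints and the sample size are unaffected.

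**What to change.** 1. Check the original page of SAP Appendix 1. If the between-day SD is printed correctly there, the main point falls away.
2. If the page shows the expression as extracted, replace it with:
   - SD = (1/n) × sum over i of SD_i
   - SD_i = sqrt( sum over k of (BG_k,i - mean over k of BG_k,i)^2 / (m-1) )
3. State that SD_i and its mean are computed over the days with a reading in each 15-minute bucket, so that m in this formula is that count, and that the between-day CV uses the same SD_i and mean.
4. Optionally, add a phrase saying whether the Week 0-12 overall SD and CV are a descriptive extra or should follow the baseline and Visit 12 windows.

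The cost is one formula and a clarifying phrase or two in Appendix 1. No new data are needed, and the sample size, primary analysis and gated testing do not change.
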